6.8 Duration of Therapy

Within three weeks of the initial treatment planning imaging study, SABR will be administered in a 1-5 fractions to each treated site (within 60 days from randomization) of the study and coincides with delivery of fraction 1.

Within four weeks of randomization to the SABR + Radium-223 arm, men will receive their 1st of 6 monthly infusions of radium-223.

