B.	Serum Chemistry (CMP) includes Sodium, Potassium, Chloride, Carbon Dioxide (bicarbonate), Urea Nitrogen, Serum Creatinine, Est GFR Afr-Am(MDRD Eqn), Est GFR NonAfrAm(MDRD Eqn), Glucose, Calcium, Total Protein, Albumin, Total Bilirubin, Alkaline Phosphatase, Aspartate Amino Trans (AST), Alanine Amino Trans (ALT), Anion Gap, BUN/Creatinine Ratio, and AST/ALT ratio.
C.	CBC w/ Diff, LDH, Serum Chemistry, and Testosterone labs must be obtained within 6 months prior to enrollment.
D.	PSA lab must be obtained within 1 month prior to enrollment.
E.	Pre-study Bone Scan and CT/MRI need to be obtained within 3 months prior to enrollment. PET-CT scan is an alternative for study entry imaging to CT/MRI and/or Bone Scan
F.	Medical history review, concomitant medication review, physical exam, performance status assessment, adverse event evaluation, and the brief pain inventory assessment should be performed once , during either Day 1 or sometime during a SBRT visit (e.g. OTV).
G.	Invitae test should be performed at any time during the study or after follow up for all enrolled patients.
H.	Correlative study blood specimens should be drawn after standard of care labs, from the same line, to prevent epithelial cells from contaminating blood specimens.
I.	CT/MRI or Axumin/Choline/DCFPyL PETs should be used to measure tumor dimensions at baseline and to measure tumor dimensions and evaluate radiographic response on day 181 and on day 361. Imaging used at baseline can be further used at Day 180 and Day 360, respectively.
J.	Instructions for CAPP-Seq Sample Collection & Processing can be found in Appendix III of the protocol.
K.	Instructions for EPIC-HD CTC Sample Collection & Processing can be found in Appendix IV of the protocol.
L.	Instructions for ImmunoSeq Sample Collection & Processing can be found in Appendix V of the protocol.
M.	Instructions for Immunophenotyping Sample Collection & Processing can be found in Appendix VIII of the protocol. Only applicable for JHU/JHSOM. Not applicable for outside sites.
N.	Instructions for Invitae Saliva Kit Sample Collection can be found in Appendix VII of the protocol.
O.	Instructions for Rectal Swab Collection for Microbiome Analysis can be found in Appendix VI of the protocol.
P.	Instructions for SBRT/SABR treatment planning can be found in section 6.3 of the protocol.

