Q.	After randomization, only interval concomitant medications, interval medical history, and limited physical exam information needs to be collected. This only needs to occur once, either on Day 1 visit or during SABR treatment.
R.	Per SOC, patient's will have a PSMA PET/CT prior to enrollment/randomization. Patients who are still enrolled in the trial will have a PSMA PET/CT 360 Days from initial PSMA PET/CT (see S).
S.	ONLY for sites participating in PSMA PET-CT: If applicable, patient's will have a PSMA PET/CT 12 Months from the second completed PSMA PET (~approximately 13/14 months from randomization)
T.	Additional follow-up visits are for 1 year. Follow up after 12 months will be conducted Q6 months, as SOC (months 18 and 24).
U.	All AEs will be collected using CTCAE version 4.0. All skeletal related events will need to be collected throughout the trial and during the follow-up period.
V.	If Pre-study and Day 1 occurs within 2 weeks of each other, the following labs do not need to be repeated for Day 1: PSA, LDH, Testosterone, CBC w/Diff, and CMP. If PSA is completed within 2 weeks from Day 1, regardless of Footnote D, then it may be used. If PSA has been drawn greater than 2 weeks from Day 1, then it must be repeated. Research Blood for Day 1 MUST be completed PRIOR to SABR and/or Xofigo (Radium-223) injection.
W.	During 18 and 24 month follow-up: limited physical exam, ECOG (performance status) changes to conmedications, changes to medical history, Adverse Events, BPI (QoL), and PSA are required for documentation (Epic Note). Any additional labs or imaging are at the discretion of the treating physician.

STUDY CALENDAR: SBRT + Xofigo ARM

	Pre-Study ^Y	Day 1 ^Y	Day 15	Day 29	Day 43	Day 57	Day 61	Day 71	Day 85	Day 31 (+/- 7 days)	Day 39	Day 113	Day 127	Day 141	Day 155	Day 181 (+/- 7 days)	Day 361 (+/- 7 days)	Follow-up Q6 Month ^W (+/- 7 days)
ICF	X																	
Demographics	X																	
Medical History	X									X ^T						X ^T	X ^T	X ^Z
Concomitant Medications	X									X ^T						X ^T	X ^T	X ^Z
Physical Exam	X									X ^T						X ^T	X ^T	X ^Z
Performance Status	X									X ^F						X	X	X ^Z
Vital Signs	X									X								
Height	X									X								
Weight	X									X								
CBC w/ Diff ^A	X ^C									X ^I						X	X	X ^Z
LDH	X ^C									X ^I						X	X	X ^Z
Serum Chemistry ^B	X ^C									X ^I						X	X	X ^Z
Testosterone	X ^C									X ^I						X	X	X ^Z
PSA	X ^D									X ^I						X	X	X ^Z
Bone Scan	X ^E									X ^I						X	X	X ^Z

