CT/MRI/Axumin or Choline PET of Involved Site ^K	X ^E									X ^I						X	X	X ^Z
PSMA-PET/CT	X ^U									X ^I								
CAPP-seq ^L										X ^H						X ^H	X ^H	
EPIC HD-CTC ^M										X ^H						X ^H		
Immuno-SEQ ^N										X ^H								
Immunophenotyping ^O										X ^H						X ^H	X ^H	
Invitae Test ^P																		
Rectal Swab ^Q																		
AE Evaluation ^X																X	X	X
QoL Brief Pain Inventory																X	X	X
SBRT/SABR ^R																		
Xofigo ^S																		

Randomization to SBRT + Xofigo arm

A.	CBC w/ Diff includes: White Blood Cell Count, Red Blood Cell Count, Hemoglobin, Hematocrit, Mean Corpuscular Volume, Mean Corpus Hgb, Mean Corpus Hgb Conc, RBC Distribution Width, Platelet Count, Neutrophils %, Lymphocyte %, Monocyte %, Eosinophil %, Basophil %, Absolute Neutrophil Count, Absolute Lymphocyte Count, Absolute Monocyte Count, Absolute Eosinophil Count, Absolute Basophil Count, Immature Granulocyte %, and Absolute Immature Granulocyte Count.
B.	Serum Chemistry (CMP) includes: Sodium, Potassium, Chloride, Carbon Dioxide (bicarbonate), Urea Nitrogen, Serum Creatinine, Est GFR Afr-Am(MDRD Eqn), Est GFR NonAfr-Am(MDRD Eqn), Glucose, Calcium, Total Protein, Albumin, Total Bilirubin, Alkaline Phosphatase, Aspartate Amino Trans (AST), Alanine Amino Trans (ALT), Anion Gap, BUN/Creatinine Ratio, and AST/ALT ratio.
C.	CBC w/ Diff, LDH, Serum Chemistry, and Testosterone labs must be obtained within 6 months prior to enrollment.
D.	PSA lab must be obtained within 1 month prior to enrollment.
E.	Pre-study Bone Scan and CT/MRI need to be obtained within 3 months prior to enrollment. PET-CT scan is an alternative for study entry imaging to CT/MRI and/or Bone Scan.
F.	Medical history review, concomitant medication review, physical exam, performance status assessment, adverse event evaluation, and the brief pain inventory assessment should be performed only once , either during Day 1 or during the SBRT visit (e.g. OTV).
G.	Invitae test should be performed at any time during the study or after follow up for all enrolled patients.
H.	Correlative study blood specimens should be drawn after standard of care labs, from the same line, to prevent epithelial cells from contaminating blood specimens.
I.	CBC w/ Diff must be performed and analyzed prior to each Xofigo infusion.

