14.1.2 Secondary Objectives

- To describe the toxicity of SABR and SABR + Radium-223 delivered for the population enrolled using grading with CTCAE v. 4.0
- To determine local control at 12-months after SABR and SABR + Radium-223 in patients with oligometastatic disease.

- To assess time to locoregional progression, time to distant progression, time to new metastasis and duration of response after randomization to SABR *versus* SABR + Radium-223.
- To assess ADT-free survival (ADT-FS) of this patient population after randomization defined as the time interval between the day of randomization and the initiation of ADT. ADT will typically be initiated on progression and/or development of new metastases.
- To assess quality of life following SABR *versus* SABR + Radium-223 arms. Brief Pain Inventory form which will be filled out by the patient at the treatment response intervals outlined above.

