14.5 Analysis of Secondary Objectives

- For safety analysis, adverse events will be summarized by type and grade.
- Kaplan-Meier (KM) estimates will be used to summarize ADT-free survival (ADT-FS), time to locoregional progression (TTLP), time to distant progression (TTDP), time to new metastasis (TNM) and duration of response over time. The median PFS, ADT-FS, TTLP, TTDP TNM and duration of response will be reported.
- The efficacy of SABR + Radium-223 in men with oligometastatic disease will also be determined by measuring local control of each lesion at 12-months.

Each metastatic lesion will be considered a target lesion and independently evaluated for response using RECIST 1.1 or bone scan evaluation criteria above. The lesion will be coded as being locally controlled if it is considered stable radiographic disease or if there is evidence of a partial or complete response. Local control assessment will start at three months following randomization and continuous assessment will be pursued during the follow-up period. The proportion of the lesions that have a stable or better response will be estimated using generalized estimating equation.

- Quality of life will be assessed using the Brief Pain Inventory form. An overall score will be calculated pre-treatment and at the time of the 2nd radiologic reassessment. The change in score will be evaluated with a paired t-test.

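### The Brief Pain Inventory score analysed as pre-treatment may be taken after SABR, and in the radium arm also after radium-223, because footnote F of both calendars permits it

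*Combined protocol and SAP*

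**What the plan says.** **Analysis.** Section 14.5 states: "An overall score will be calculated pre-treatment and at the time of the 2nd radiologic reassessment". It continues: "The change in score will be evaluated with a paired t-test". No between-arm test of the BPI is named.

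**Collection.** Footnote F of the SBRT-only calendar in section 8 groups the BPI with history, medication review, examination, performance status and adverse-event evaluation. The group is to be done once, "during either Day 1 or sometime during a SBRT visit (e.g. OTV". Footnote F of the SBRT + Xofigo calendar gives the same choice: "either during Day 1 or during the SBRT visit (e.g. OTV". OTV is not in the abbreviation list; I read it as on-treatment visit. Section 14.1.2 adds only this: "Brief Pain Inventory form which will be filled out by the patient at the treatment response intervals outlined above". That sets no pre-treatment window.

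**Treatment timing.** Section 6.8 allows SABR "within 60 days from randomization) of the study and coincides with delivery of fraction 1". For radium it says: "Within four weeks of randomization to the SABR + Radium-223 arm, men will receive" the first of six infusions. Section 6.4 sets the interval at four weeks.

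**Where the plan does protect a baseline.** Footnotes V (SBRT-only) and Y (SBRT + Xofigo) state: "Research Blood for Day 1 MUST be completed PRIOR to SABR and/or Xofigo (Radium-223) injection". Section 6.7.3 likewise places the enrolment rectal swabs before SABR or radium.

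**The concern.** The analysis needs a score from before treatment, and the collection rule does not deliver one. A site can follow footnote F exactly and return a form completed after SABR has begun. The paired test would then use that form as its baseline, and any effect of treatment already present on that day would be subtracted from the later score.

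In the radium arm the same form may also follow radium-223, which cannot happen in the SABR-only arm. The synopsis and section 14.1.2 word the quality-of-life objective as SABR versus SABR + radium-223. Any descriptive comparison of change between arms would therefore start from baselines with different prior exposure to the agent under study.

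**Working it through.** The plan states no sample size, power or effect size for the BPI, so there is no figure to reproduce. The check has three steps.

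**1. Does any other text put the BPI before treatment?**
- Section 6.2 defines Day 1 only as falling within 30 days of randomization. It does not say that Day 1 precedes treatment.
- The registration documents in 6.1.2 and the pre-treatment list in 6.4 do not mention the BPI.
- Footnotes Q (SBRT-only) and T (SBRT + Xofigo) allow the companion interval assessments on Day 1 or during SABR, so the on-treatment option looks intended.
- The explicit before-treatment rule covers research blood and rectal swabs, not the BPI.

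No text closes the gap.

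**2. How many infusions can precede a BPI at a SABR visit?**

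Inputs: first infusion on day f after randomization, f = 0 to 28 (6.8); interval 28 days (6.4); SABR visit on day s, up to day 60 (6.8). Infusion k falls on day f + 28(k − 1). Count those on or before day s.

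For s = 60:
- Infusion 1: f ≤ 60, always.
- Infusion 2: f + 28 ≤ 60, so f ≤ 32, always.
- Infusion 3: f + 56 ≤ 60, so f ≤ 4.
- Infusion 4: f + 84 ≤ 60, never.

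The count is three for a first infusion on days 0 to 4 and two for days 5 to 28. If the interval is taken as 30 days, three is reached only for f = 0; at 31 days the maximum is two.

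For s = 30, the limit if section 6.2's 30 days for Day 1 governs: infusion 2 needs f + 28 ≤ 30, so f ≤ 2, and infusion 3 is never reached. The maximum is two.

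With infusions on schedule, any radium-arm BPI at a SABR visit after day 28 follows at least one infusion, and any after day 56 follows at least two. In the SABR-only arm the count is zero for every s, and prior exposure is SABR fractions only.

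**3. What does this do to the change score?**

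Let p be the share of men whose baseline form postdates first treatment, and d the mean shift that treatment has caused in their score by then.

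- Mean recorded baseline = true baseline + p × d
- Mean observed change = true change − p × d

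The documents give neither p nor d, nor the sign of d. As a labelled assumption only, take p = 0.25 to 1 and d = 0.25 to 0.5 SD of the change score in absolute size. The bias then runs from 0.25 × 0.25 = 0.06 SD to 1 × 0.5 = 0.50 SD. For scale, a paired test with 32 men detects about (1.960 + 0.842)/√32 = 0.50 SD at two-sided 5% and 80% power, both also assumed. Under these assumptions the bias could be trivial or as large as the detectable effect.

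**The case against.** The strongest reply is that section 14.5 already says the score is pre-treatment, and that Day 1 is the first option in footnote F. A form from Day 1, or one completed before a single fraction at the SABR visit, may be valid. Case report form deadlines also discourage a very late baseline: four weeks after randomization in 12.1, and 14 days after registration for the Baseline Assessment Form in 12.3. This stands to the extent that the fault is permitted rather than certain. It does not remove the fault. The documents do not say which form carries the BPI, and treatment can begin inside both deadlines.

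Four stronger readings are tempting and should not be drawn:

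- **That adverse-event baselines are compromised too.** Footnote F does not call its adverse-event evaluation a baseline. Section 10.5.1.2 records events from consent. History, examination and performance status are taken at Pre-Study, and section 6.4 requires toxicity evaluation during treatment. Moving that evaluation would work against the plan.
- **That the calendars schedule no Pre-Study BPI.** The grids are broken in the text available: the BPI row of the SBRT-only calendar is entirely blank, although footnote W requires the form at months 18 and 24. A missing mark proves nothing.
- **That on-treatment symptoms make later scores look better.** The form has no fatigue item, and its mood item asks only about interference from pain. Worst pain, least pain and interference use a 24-hour recall, so a form completed at a single-fraction visit may largely describe the time before it. Asymptomatic metastases at entry (5.1.1) make that direction plausible but do not establish it.
- **That the treatment comparison is biased.** Prior exposure can differ by arm, but 14.5 specifies no between-arm BPI test.

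**Conclusion.** The point holds for the BPI alone. Section 14.5 requires a pre-treatment score, while footnote F of both calendars allows the single early form at an on-treatment visit. The baseline may follow SABR in either arm and, in the radium arm only, one or more infusions. Three prior infusions is an extreme case: it needs the first infusion on days 0 to 4, SABR near day 60 and a BPI not done on Day 1. Otherwise the maximum is two. These counts assume on-schedule infusions and the 60-day window in 6.8. That window sits awkwardly beside the 30 days in 6.2, and the two passages need reconciling.

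The firm harm is to the within-patient change and to any descriptive comparison of arms. No size or direction can be taken from the documents, and the SD range above is illustration only. This is a secondary endpoint and the primary PFS analysis is untouched. The correction is still worth making, because the rule as written defeats the stated analysis and repair is nearly free.

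**What to change.** - **Footnote F, both calendars, BPI only:** remove the SBRT-visit/OTV option. Require the form after consent and before the first SABR fraction or first radium-223 injection, whichever comes first, using the wording already applied to research blood in footnotes V and Y.
- **Section 14.5:** define baseline BPI as the last form completed before that point, and state that later forms are not used as baseline.
- **Adverse-event evaluation:** leave it at treatment visits, unchanged.
- **Forms already collected:** compare each form date with the date of first treatment, and report by arm how many men have a valid baseline.

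The cost is two footnote edits and one sentence in 14.5, plus a date check on existing forms. The form is completed by the patient and can be done at the pre-study visit or before treatment on Day 1. No visit is added and no clinical rule changes. Men without a valid baseline drop out of the paired analysis.

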9. MEASUREMENT OF EFFECT

9.1 Antitumor Effect – Metastatic Tumors

For the purposes of this study, patients should be re-evaluated for radiographic response 6- and 12-months after randomization. Trial radiologists evaluating for treatment responses will be blinded to the treatment group and treatment specifics (lesions treated with SABR).

Response and progression will be evaluated in three ways:

- 1) Using Response Evaluation Criteria in Solid Tumors (RECIST 1.1) Committee definition. Changes in only the largest diameter (uni-dimensional measurement) of the tumor lesions are used in the RECIST criteria.
- 2) Lesions by bone scan will be evaluated as positive, negative or no change. MRI of the bone lesion can be used to clarify equivocal lesions.
- 3) Serial PSA changes.

9.2 Definitions

Evaluable Population: will consist of all patients who have received SABR.

Safety Population: Will consist of all subjects who were enrolled and have undergone at least one fraction of SABR. This will be used to assess the clinical safety and tolerability of the study.

Evaluable for Objective Response: Only those patients who have measurable disease present at baseline, have completed all fractions of SABR, and have had their disease re-evaluated will be considered evaluable for response. These patients will have their response classified according to the definitions stated below.

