CORRELATIVE SCIENCE	
• To enumerate circulating tumor cells (CTC) using EPIC HD-CTC platforms at baseline, months 3, 6 and 12 from randomization.• To enumerate circulating tumor DNA (ctDNA) using Cancer Personalized Profiling by deep sequencing (CAPP-Seq) at baseline, months 3, 6 and 12 from randomization for SABR versus SABR + Radium-223.• To quantitatively sequence T-cell receptor (TCR) repertoires using peripheral blood monocytes and the ImmunoSEQ platform at baseline, months 3, 6 and 12 from randomization.• To evaluate immunophenotypes by running PBMCs through a Cytek Aurora machine, which allows for simultaneous detection of up to 25 markers; to evaluate metabolic fitness of the total PBMCs using the mitochondrial stress test on the Seahorse analyzer; and to determine the relative capacity of peripheral T cells to metabolically respond to T cell receptor stimulation through activation of CD3 and CD28 by running functional assays on PBMCs.• To determine frequency of germline DNA repair mutations in the oligometastatic state• Descriptive statistics will be performed to correlate the metrics above with clinical outcomes.
HYPOTHESES	SABR + Radium-223 will increase median progression-free survival from 10 months in the SABR arm to 20 months in the SABR + Radium-223 arm
STUDY DESIGN	Men with oligometastatic prostate cancer lesions will be randomized (1:1) to SABR versus SABR + Radium-223. The study will NOT be blinded. Within three weeks of the initial treatment planning, SABR(1-

	5 fractions) will be administered for all men. For the SABR + Radium-223 the 1 st radium-223 infusion will be within four weeks from randomization.
SAMPLE SIZE BY TREATMENT GROUP	64 patients total
SUMMARY OF SUBJECT ELIGIBILITY CRITERIA	
 1. Metastatic bone or nodal sites \leq 3 on standard imaging (or \leq 5 on Axumin, Choline with at least one bone metastasis. 2. PSA DT $<$ 15 months 3. Tumor \leq 5.0 cm or $<$ 250 cm³. 4. Age \geq 18 years. 5. ECOG performance status \leq 2. 6. Histologic confirmation of malignancy (primary or metastatic tumor).
CONTROL GROUP	N/A

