6.1.1 General Guidelines

Eligible patients will be entered on study centrally at the Sidney Kimmel Comprehensive Cancer Center at the Johns Hopkins University by the Lead Study Coordinator, [name]. All sites should call/email the coordinating

center at [contact] for registration. The Eligibility Worksheet will be supplied to each participating site.

Subjects who sign a consent form, but do not initiate protocol treatment for any reason (e.g., subjects who are screen failures), will be replaced and will not count towards our accrual goal. The Coordinating Center should be notified as soon as possible.

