6.11 Criteria for Patient Removal

Diagnosis of >3 bone and/or soft tissue metastases on entry imaging studies before SBRT/SABR. PSA >50 ng/ml before SABR. Progression as defined in section 9.5.5.

Radium-223 administration may be delayed by no more than four weeks for recovery of adverse events. In case of a treatment delay greater than four weeks, treatment should be discontinued. It is important to note that in general (unless otherwise agreed), in cases where study drug has been ordered, the time window is reduced to -3 days to + 3 days, due to decay. If administration has to be postponed more than 3 days after drug has been ordered, replacement of the drug order is required. Dose reduction for radium-223 will not be permitted and subjects with any toxicity requiring radium-223 dose reduction must discontinue radium-223 treatment.

Any toxicity requiring radium-223 discontinuation will be recorded as an AE in the subject's medical record and on the CRF.

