10.2 Definitions

10.2.1 Adverse Event (AE)

An adverse event is any undesirable sign, symptom or medical condition or experience that develops or worsens in severity after starting the first dose of study treatment or any procedure specified in the protocol, even if the event is not considered to be related to the study.

Abnormal laboratory values or diagnostic test results constitute adverse events only if they induce clinical signs or symptoms or require treatment or further diagnostic tests.

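### The safety set in 9.2 is defined by SABR alone and does not match 14.6, so a man given radium-223 who never reaches SABR can drop out of the toxicity summary

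*Combined protocol and SAP*

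**What the plan says.** Section 9.2 defines the safety population as follows: "Will consist of all subjects who were enrolled and have undergone at least one fraction of SABR". It adds that this set is the one for judging safety and tolerability. Section 14.5 says that adverse events will be summarized by type and grade but names no population, so 9.2 supplies it. Section 14.6 gives its own rule for who is evaluable for toxicity. It asks for at least one SABR fraction and joins SABR to radium-223 with the word *and*.

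On timing, 6.8 states for the combination arm: "Within four weeks of randomization to the SABR + Radium-223 arm, men will receive their 1st of 6 monthly infusions of radium-223". The synopsis agrees: "radium-223 infusion will be within four weeks from randomization". For SABR, 6.8 gives a longer window in a sentence that is hard to parse: "within 60 days from randomization) of the study and coincides with delivery of fraction 1".

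Three other sections bear on how a man given radium-223 only is treated:

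- Section 10.2.1 counts an adverse event as one that "develops or worsens in severity after starting the first dose of study treatment or any procedure specified in the protocol", with no SABR condition.
- Section 6.1.1 says that men who "do not initiate protocol treatment for any reason (e.g., subjects who are screen failures), will be replaced and will not count" toward accrual. A man who has had an infusion has started protocol treatment, so he is not replaced.
- Section 14.1.2 states the toxicity objective: "To describe the toxicity of SABR and SABR + Radium-223 delivered for the population enrolled".

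**The concern.** Radium-223 is the agent under test, and toxicity is the first-listed secondary objective. A safety set for this trial should hold every man exposed to either protocol treatment. The 9.2 set is keyed to SABR, the treatment common to both arms, and so can lose a man exposed to radium-223.

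The loss is one-sided. A control-arm man who misses SABR has received no protocol treatment and is properly left out. A combination-arm man who misses SABR may already have had one or more infusions. If early toxicity or death is why he missed SABR, leaving him out lowers the reported toxicity rate for the combination. If he left without an event, leaving him out raises it slightly.

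**Working it through.** The plan states no figure on this point, so there is none to reproduce. The check compares the definitions, then the treatment windows, then the possible size of the effect.

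**1. Who is in each set, by treatment received**

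| Received | 9.2 | 14.6, literal (both treatments) | 14.6, distributive (either treatment) |
|---|---|---|---|
| SABR only | in | out | in |
| SABR and radium-223 | in | in | in |
| Radium-223 only | out | out | in |
| Neither | out | out | out |

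Neither reading of 14.6 gives the same set as 9.2. The literal reading drops the control arm, which contradicts 14.1.2, where toxicity is wanted for both regimens. The distributive reading is the only one consistent with 14.1.2, and it differs from 9.2 in exactly one row: the man given radium-223 only.

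**2. Can radium-223 come first?**

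Inputs: first infusion on day s, with s from 0 to 28 (6.8); infusions every 28 days (6.4, Dosage); SABR by day 60 (6.8). Infusions fall on day s + 28k, counted if strictly before SABR.

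- SABR on day 60: for s = 0 to 3, three infusions come first (s = 3 gives days 3, 31, 59). For s = 4 to 28, two come first (s = 28 gives days 28, 56). The gap from first infusion to SABR is at least 60 − 28 = 32 days.
- SABR on day 30, if the 30-day Day 1 window in 6.2 governs instead: two infusions for s = 0 to 1 and one for s = 2 to 28.

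These are limits of what the text permits, not the expected course.

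**3. Can a man stop in between?**

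Section 6.11 lists a removal criterion set in that interval: "PSA >50 ng/ml before SABR". It also lists progression. Section 6.15 adds withdrawal of consent and withdrawal by the investigator for adverse events. Death is also possible.

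**4. Size, by illustration**

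Assumed: 32 men treated in the combination arm (the number per arm in 14.2), 3 of them with a given toxicity. True rate: 3/32 = 9.4%.

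| Men omitted | Of whom with the event | Reported rate |
|---|---|---|
| 1 | 1 | 2/31 = 6.5% |
| 1 | 0 | 3/31 = 9.7% |
| 2 | 2 | 1/30 = 3.3% |
| 2 | 1 | 2/30 = 6.7% |
| 2 | 0 | 3/30 = 10.0% |

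The 3.3% row needs two of the arm's three events to fall in men who never had SABR. It shows what is possible, not what is likely.

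**The case against.** The strongest reply is that 14.6 already covers this man. Its literal reading would remove the whole control arm, so the authors must have meant the distributive one, and that admits him. This largely stands. A reader might infer from 9.2 that his exclusion is certain; the documents do not support that. They support a conflict between two definitions, one of which leaves him out.

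The second reply is that the case is hard to reach. Section 6.2 places Day 1 of both arms within 30 days of randomization. The 60-day sentence in 6.8 is garbled and may tie Day 1 to the first SABR fraction. The calendar columns at days 1, 29, 57, 85, 113 and 141 fit six infusions starting on Day 1, so a near-concurrent start may be usual. The marks in the SABR and Xofigo calendar rows are missing from the text as read, so the planned order cannot be confirmed from it. This also stands, and it bears on frequency. It does not remove the gap, because no text found requires SABR first.

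Third, nothing makes SABR depend on blood counts or on tolerance of radium-223; the toxicity rules in 6.4 and 6.11 delay or stop radium-223. Loss of SABR through toxicity is therefore possible under 6.15 but is not a protocol rule. The limit on metastases in 6.11 concerns entry imaging and would seldom apply after an infusion.

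Fourth, the wording of 14.1.2 about the enrolled population might be taken to require his inclusion. It does not clearly do so: the sentence concerns SABR and SABR + Radium-223 as delivered, and he received neither complete regimen.

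**Conclusion.** The point holds at minor severity. Sections 9.2 and 14.6 do not define the same set, and 9.2 leaves out a man exposed to radium-223 who has no SABR fraction. Such men are probably few; the documents give no rate. Any bias is confined to the descriptive toxicity summary, can arise in the combination arm only, and can run in either direction.

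A reader might infer more than this, and the documents do not support it:

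- Safety data are not lost. Section 10.5.1.2 records adverse events from consent and sends all serious ones to the coordinating center within 24 hours, and 10.3 asks for observations throughout the two years.
- The stopping rule is not shown to be affected. Section 14.3 is written for the SABR + Radium-223 arm and does not cite the 9.2 set.
- The primary analysis is not affected. Section 14.4 analyses PFS in all randomized men.
- A systematic understatement of toxicity is not established. It would require that men missed SABR because of toxicity or death.

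The conclusion rests on two readings: that the 60-day limit in 6.8 applies to SABR, and that no sequence rule exists elsewhere. If the 30-day window governs instead, radium-223 can still come first, with fewer prior infusions.

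**What to change.** In 9.2 and 14.6, use one definition: all randomized men who received at least one fraction of protocol SABR or at least one protocol radium-223 infusion, with follow-up for toxicity from the first of either. Tabulate by protocol treatment received, so that any protocol radium-223 places a man in the SABR + Radium-223 group and SABR alone places him in the SABR group. The word *protocol* matters: without it, a control man given radium-223 later, off study, would move into the combination group. No change to 14.3 is needed.

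The cost is one sentence in each of the two sections. No new data are required, because adverse events are already recorded from consent, and the sample size and power are unchanged. The one downside is that the reported toxicity rate may shift slightly, in either direction.
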